Approved staff from the VA Salt Lake City (VASLC) will transcribe the non-identifiable audio recordings of participants' workshop feedback. The VASLC has a Professional Transcription Service available to VA sites and monitored by their own IRB. The study audio recordings to be transcribed by VASLC staff will be labeled by the subject's unique ID number and saved behind the VA Firewall in secure shared project folder ([name] Transcriptions) on the M- Drive of the VA computer. The VASLC transcription staff will be given access to a sub-folder within the secure project folder. Approved study staff will place a copy of the audio files in this folder for an approved VASLC transcriptionist to access for the purposes of transcription. The VASLC transcriptionist will transcribe each interview verbatim and save the completed transcript in the sub-folder using the same ID number. No data (audio files, in process transcripts, or completed transcripts) will leave the MEDVAMC secure research server. As completed transcripts become available, approved study staff will move these files from the transcription sub-folder into another sub-folder that is only accessible to study staff, where they will be stored and accessed for qualitative analyses.

Section L: Cost/Payment

Delineate clinical procedures from research procedures. Will subject's insurance (or subject) be responsible for research related costs? If so state for which items subject's insurance (or subject) will be responsible (surgery, device, drugs, etc). If appropriate, discuss the availability of financial counseling.

Subjects will not be responsible for research related costs.

If subjects will be paid (money, gift certificates, coupons, etc.) to participate in this research project, please note the total dollar amount (or dollar value amount) and distribution plan (one payment, pro-rated payment, paid upon completion, etc) of the payment.

Dollar Amount:

155

Distribution Plan:

Enrolled participants will be paid \$100 for completing assessments over the course of the study (\$30 for baseline, \$20 for 2 week follow-up, \$20 for 6 week follow-up, and \$30 for 3 month follow-up). We have also allocated \$25 per participant for meals and snacks during the 6-hour workshop. Participants will also be reimbursed up to \$30 per participant for mileage during in-person visits (for anyone living outside the immediate Houston area). (\$6000 or \$3,000 in each year of the project)

Section M: Genetics

How would you classify your genetic study?

Discuss the potential for psychological, social, and/or physical harm subsequent to participation in this research. Please discuss, considering the following areas: risks to privacy, confidentiality, insurability, employability, immigration status, paternity status, educational opportunities, or social stigma.

Will subjects be offered any type of genetic education or counseling, and if so, who will provide the education or counseling and under what conditions will it be provided? If there is the possibility that a family's pedigree will be presented or published, please describe how you will protect family member's confidentiality?

Section N: Sample Collection

None

Section O: Drug Studies

Does the research involve the use of ANY drug* or biologic? (*A drug is defined as any substance that is used to elicit a pharmacologic or physiologic response whether it is for treatment or diagnostic purposes)

No

Does the research involve the use of ANY gene transfer agent for human gene transfer research?

No

O1. Current Drugs

Is this study placebo-controlled?

No

Will the research involve a radioactive drug that is not approved by the FDA?

No

Section P: Device Studies

Does this research study involve the use of ANY device?

No

Section Q. Consent Form(s)

None

Section R: Advertisements

Mode of Advertising: Other: Brochures

Exact language of Advertisement:

If the adjustment back to civilian life has been challenging, consider participating in a new study at the Michael E. DeBakey VA Medical Center.

What is the goal of the study? The goal of this study is to better understand the experiences of returning OIF/OEF/OND Veterans and to provide strategies to help Veterans develop resilience and adjust to new challenges.

What will happen during the study? If you agree to take part in this study, you may be invited to an 1-day group workshop with other Veterans who have had similar experiences. During the workshop, strategies and skills will be taught on how to develop resilience in the face of stress and difficulty

How do I join? Call [contact] to discover if you are eligible. If we are unable to answer your call, please leave a message and we will return your call promptly.

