Pilot 2. For the second pilot, all following Veterans who are eligible will be randomized at a 2:1 ratio to either the workshop group or treatment as usual group (TAU). These Veterans will also complete 2, 6, 12 week follow-up assessments. Veterans who were assigned to the workshop will also provide feedback about the workshops.

All participants will be given the opportunity to ask questions at any time throughout the study and will be reminded that participation is completely voluntary. They will also be told that this study will not affect their hospital care in any way.

Inclusion Criteria:

1) 18-60 years of age, 2) Clinically significant psychological distress as operationalized by a diagnosis of major depressive disorder, generalized anxiety disorder, or PTSD, 3) Life time history of Mild TBI; 4) Presence in medical chart of chronic pain including headache, musculoskeletal pain or neuropathic pain; 5) Stable dose of psychiatric medications for the past 4 weeks.

Exclusion Criteria:

1) History of primary psychotic disorder (e.g., schizophrenia, schizoaffective disorder); 2) a diagnosis of substance dependence in the year prior to enrollment in the study; 3) Active suicidal ideation; 4) Homicidal ideation.

F2. Procedure

Participants who are interested in the study will complete a brief (5 minute) screening (see attachment) either in-person or over the phone. This takes place even prior to consent. If screening criteria are met, the patient will be invited to the clinic for an in-person assessment/interview phase. At the beginning of the in-person visit, the consent document will be reviewed with the patient and all questions pertaining to the study will be answered. If the patient is interested in the study, he/she will sign the consent and complete an assessment. The initial assessment will take approximately 3 hours to complete.

The following measures will then be completed:

Clinical Interviews. The Structured Clinical Interview for DSM-IV Axis I Disorders (SCID-IV) will be used to assess major DSM-IV Axis I diagnoses, including mood disorders, anxiety disorders, and other psychiatric disorders; the Clinician Administered PTSD Scale (CAPS), the gold standard in PTSD assessment, will be used to make a current, post-deployment, and/or lifetime diagnosis of PTSD. The Boston Assessment of TBI-Lifetime (BAT-L) will be used to determine history of blast exposure and subsequent blast-related TBI.

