At baseline, pattern separation task will also be completed where participants will be shown pictures of everyday objects and asked to indicate if the picture is old, new, or similar which provides an assessment of memory performance. The delay between first presentation and repeated presentation of a lure or repeated image will vary. Images remained on the screen for 2 seconds, followed by a 500 millisecond inter-stimulus interval. Participants will view a total of 324 images.

Self-Report Measures. Demographic questionnaire - The Depression Anxiety and Stress Scale (DASS-21) - The PTSD Checklist - Civilian Version (PCL) - The McGill Pain Questionnaire - The Brief Pain Inventory (BPI) - The World Health Organization Disability Assessment Schedule II (WHODAS-II) - The World Health Organization-Quality of Life (WHO-QOL) - The Military to Civilian Questionnaire (M2C-Q) - Medication usage and therapy involvement - Brief Religious Coping Scale (R-COPE) - Chronic Pain Acceptance Questionnaire (CPAQ) - Cognitive Fusion Questionnaire (CFQ-13) - Acceptance and Action Questionnaire (AAQ-II) - Experiences Questionnaire (EQ) - Chronic Pain Values Inventory (CPVI) - Pain Intensity - Committed Action Questionnaire (CAQ) - Trauma Recovery Scale, Part III (TRS) - Impact of Events Scale (IES) - Social Network Index (SNI) - UCLA Loneliness Scale - Moral Injury Scale (MIS)

Treatment: Pilot 1. If the assessment confirms the presence of psychopathology and mTBI, the patient will be invited to attend a workshop called ACT on Life based on Acceptance and Commitment Training (ACT). 10 Veterans will complete this ACT on Life Workshop.

Workshop: Patients in the ACT condition will attend a 1-day group workshop. Each ACT group will be held at MEDVAMC, include 5-8 patients, and will last 6 hours. The ACT group will be conducted by the PI and a doctoral level psychologist or advanced doctoral student. The intervention includes: 1) Behavioral Change Training (2 hours) involving a) teaching patients how to recognize ineffective patterns of behavior and habits, b) exploring

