and setting life goals and goals related to mental and physical health, and c) promoting effective and committed actions to achieve these goals despite the urge to do otherwise; 2) Mindfulness and Acceptance Training (2 hours) emphasizing new ways of managing troubling thoughts, feelings, and physical sensations (e.g., learning how to recognize, and develop cognitive distance from unhelpful thoughts such as „I can’t take this pain anymore, or „I am not good enough,) and learning how to face willingly experiences that cannot be changed; and 3) Education about PTSD, TBI, and chronic pain conditions (2 hours).

A total of 10 Veterans will complete the ACT on life Workshop in Pilot 1. These 10 Veterans will provide feedback about the workshop at 2-weeks and 12-week follow-up visits. The feedback will be used to make modifications to the ACT on Life workshop so that it is more Veteran-centric. All following eligible Veterans will be part of Pilot 2.

Pilot 2. If the assessment confirms the presence of psychopathology and mTBI, the patient will be randomized into either the ACT workshop or treatment as usual condition (TAU). The ACT workshop will be similar to that described above but will incorporate feedback from Veteran who completed Pilot 1 and any additional edits from the expert team.

An individualized phone booster session will take place 3-4 weeks following the workshop. During the phone call, we will ask participants if they are using the strategies taught, troubleshoot difficulties, and review some of the main concepts taught in the workshop. The booster session interview guide is attached.

Follow-up: At 2 weeks, 6 weeks, and 12 weeks, following the workshop, patients in both the ACT and Treatment as Usual (TAU) groups will complete assessments over the phone or in-person.

The follow-up assessments are expected to take 1 hour and are attached.

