At the 2-week follow-up, the following self-report measures will be completed: Chronic Pain Acceptance Questionnaire (CPAQ) - Chronic Pain Values Inventory (CPVI) - Acceptance and Action Questionnaire (AAQ-II) - Experiences Questionnaire (EQ) - Group Climate Questionnaire (GCQ) - Client Satisfaction Questionnaire (CSQ) - Feedback about workshop - Pain Intensity Scale - Therapy and medication usage - Committed Action Questionnaire (CAQ) - Cognitive Fusion Questionnaire (CFQ-13) - Brief Religious Coping Scale (R-COPE) - Trauma Recovery Scale, Part III (TRS) - Impact of Events Scale (IES) - Social Network Index (SNI) - UCLA Loneliness Scale .

Feedback about the workshop will also be obtained from the Veterans.

At the 6-week follow-up, the following self-report measures will be completed: Chronic Pain Acceptance Questionnaire (CPAQ) - Chronic Pain Values Inventory (CPVI) - Acceptance and Action Questionnaire (AAQ-II) - Experiences Questionnaire (EQ) - Pain Intensity Scale - Therapy and medication usage -Committed Action Questionnaire (CAQ) - Cognitive Fusion Questionnaire (CFQ-13) - Brief Religious Coping Scale (R-COPE) - Trauma Recovery Scale, Part III (TRS) - Impact of Events Scale (IES) - Social Network

Index (SNI) - UCLA Loneliness Scale

At the 12-week follow-up, the following will be completed: Clinical Interviews. The Structured Clinical Interview for DSM-IV Axis I Disorders (SCID-IV) - the Clinician Administered PTSD Scale (CAPS). Feedback about the workshop will also be obtained from the Veterans.

The pattern separation task will again be repeated at the 12 week follow-up.

Self-Report Measures. The Depression Anxiety and Stress Scale (DASS-21) -The PTSD CheckList ζ Civilian Version (PCL) - The McGill Pain Questionnaire - The Brief Pain Inventory (BPI) - The World Health Organization Disability Assessment Schedule II (WHODAS-II) - The World Health Organization-Quality of Life (WHO-QOL) - The Military to Civilian Questionnaire (M2C-Q) - Medication usage and therapy involvement - Brief Religious Coping Scale (R-COPE) - Chronic Pain Acceptance Questionnaire (CPAQ) - Cognitive Fusion Questionnaire (CFQ-13) - Acceptance and Action Questionnaire (AAQ-II) - Experiences Questionnaire (EQ) - Chronic Pain Values Inventory (CPVI) - Pain Intensity - Committed Action Questionnaire (CAQ) - Trauma Recovery Scale, Part III (TRS) - Impact of Events Scale (IES) - Social Network Index (SNI) - UCLA Loneliness Scale.

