Assessments and the treatment intervention will be audio-recorded. The audio recordings will be used for 1) assessment of treatment integrity (i.e., to ensure that therapists are following study procedures) and 2) for inter-rater reliability of the clinical interviews.

Section G: Sample Size/Data Analysis

G1. Sample Size

How many subjects (or specimens, or charts) will be used in this study?

Local: 80 Worldwide: 80

Please indicate why you chose the sample size proposed:

80 Veterans with mTBI, stress-based psychopathology, and pain will be enrolled in this research study.

Initially, ten Veterans will be enrolled in the ζ ACT on Life ζ workshop and the PI will obtain their feedback on the intervention so that it may be adapted and refined to meet the unique needs of OIF/OEF/OND Veterans with these comorbid conditions; all remaining eligible and interested Veterans will be randomized at a ratio of 2:1 to the refined ζ ACT on Life ζ workshop or TAU in order to obtain preliminary data on the efficacy of this workshop on quality of life, functioning, distress, and pain interference.

Recruitment feasibility of approximately 4 subjects per month over the study period and budgetary restrictions were the main considerations for sample size determination. This study has adequate (i.e., 80%) power to detect at least Cohen's $d_s > 1$ (i.e., large effect sizes) at a 5% significance level. Previous research has established that, when compared with TAU, ACT interventions have clinically relevant moderate effect sizes (i.e., smaller than the

effects this study is powered to detect). Thus, this study is underpowered to show clinically meaningful efficacy of ACT when compared to TAU. However, this is not an issue given the pilot nature of this RCT. This pilot RCT will allow to determine feasibility of a larger well-powered RCT. For instance, this pilot RCT will allow the PI to determine if recruitment, participants, randomization willingness and follow-up retention rates estimates are as anticipated and can be applied in the planning of a larger RCT in this population for which ACT will be developed for the first time in Aims 1 and 2 of this proposal.

G2. Data Analysis

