Provide a description of your plan for data analysis. State the types of comparisons you plan (e.g. comparison of means, comparison of proportions, regressions, analysis of variance). Which is the PRIMARY comparison/analysis? How will the analyses proposed relate to the primary purposes of your study?

Frequency data will be gathered on the number of veterans screened for participation and the number willing to participate in the study, the number of Veterans who are not eligible to participate and the reasons for lack of eligibility will also be tracked to identify the proportion of Veterans who may have difficulties and may be in need of an intervention.

We hypothesize that at 3-month follow-up, Veterans randomized to ACT on Life will experience greater improvements in Quality of life (WHO-QOL), functioning (WHODAS-II), distress (DASS-21), and pain-interference (BPI) compared to the TAU group. Data collected at baseline, 2-, 6- and 12-weeks follow-up for each of the aforementioned outcomes of interest will be compared between the groups using a generalized linear mixed model (GLMM) that can accommodate repeated measures over time and missing data due to loss to follow-up or missed interviews. Based on our previous experience with this population and the high retention rates for 1-day ACT trials, we anticipate a 10% loss-to-follow-up rate at the 12-week evaluation. The GLMM model for each outcome will include group, week (continuous outcome) and group by week interaction as the predictors. The influence of key demographic variables (e.g., age, rural/urban, gender) on the outcomes of interest will also be explored by adding these variables as predictors to the linear models.

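### Does timing both arms' follow-up from the workshop leave treatment-as-usual Veterans without a start date?

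*Combined protocol and SAP*

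**What the plan says.** The F2 follow-up paragraph names a starting point for the assessments and applies it to both arms: "At 2 weeks, 6 weeks, and 12 weeks, following the workshop, patients in both the ACT and Treatment as Usual (TAU) groups will complete assessments". Elsewhere the schedule has no origin. F1, under Pilot 2, says only "These Veterans will also complete 2, 6, 12 week follow-up assessments", and G2 refers to "Data collected at baseline, 2-, 6- and 12-weeks follow-up for each of the aforementioned outcomes of interest".

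Allocation is one or the other: "the patient will be randomized into either the ACT workshop or treatment as usual condition (TAU". No section gives TAU Veterans a workshop, then or later. On the workshop, F2 says "Each ACT group will be held at MEDVAMC, include 5-8 patients, and will last 6 hours", and G1 gives the pace of enrolment as "Recruitment feasibility of approximately 4 subjects per month over the study period". Allocation is 2:1 in favour of ACT (F1, G1).

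On the analysis, G2 says "The GLMM model for each outcome will include group, week (continuous outcome) and group by week interaction as the predictors". It does not say whether week is nominal or actual time, or from which date it runs. The document also has no visit windows and no rule for an ACT Veteran who misses the workshop.

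**The concern.** Read literally, the rule counts TAU visits from an event that TAU Veterans do not attend. If staff filled the gap by timing TAU from randomisation and ACT from the workshop, the two arms would be observed over different lengths of time after baseline. Background change over the extra weeks in ACT would then be mixed with the treatment effect.

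The hypothesised outcomes make this look more serious. The F2 baseline and 12-week lists include DASS-21, BPI and "The World Health Organization Disability Assessment Schedule II (WHODAS-II) - The World Health Organization-Quality of Life (WHO-QOL"), while the 2- and 6-week lists include none of these four. On those lists, each arm's result rests on a single interval. If its length differed by arm and the model used nominal week, the difference would not show. The trial is meant to inform a larger one, so a distorted preliminary effect or an ill-defined 12-week retention rate would carry forward.

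**Working it through.** The plan states no figure for this interval, so there is none to reproduce. The check sizes the unfavourable reading and then sets it against the text.

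**Inputs**
- Enrolment: about 4 per month (G1).
- Share to ACT: 2/3, from the 2:1 ratio (F1, G1).
- Workshop size g: 5 to 8 (F2).
- Last visit: 12 weeks (F2).
- Conversion: 4.348 weeks per month.

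**Reading A: ACT timed from the workshop, TAU from randomisation**

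This needs four assumptions that are not in the document: steady accrual, randomisation soon after baseline, a workshop held only when its places fill, and TAU timed from randomisation.

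- ACT accrual: 4 × 2/3 = 2.67 per month; 2.67 / 4.348 = 0.613 per week.
- Wait of the first member, (g − 1) / 0.613: 4 / 0.613 = 6.5 weeks for g = 5; 7 / 0.613 = 11.4 weeks for g = 8.
- Mean wait, half of that: 3.3 and 5.7 weeks.

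| Visit, weeks from baseline | ACT, g = 5 | ACT, g = 8 | TAU |
|---|---|---|---|
| 2-week, mean | 2 + 3.3 = 5.3 | 2 + 5.7 = 7.7 | 2 |
| 12-week, mean | 12 + 3.3 = 15.3 | 12 + 5.7 = 17.7 | 12 |
| 12-week, first member | 12 + 6.5 = 18.5 | 12 + 11.4 = 23.4 | 12 |

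The mean ACT interval is then 27% to 48% longer than the TAU interval (15.26 / 12 = 1.27; 17.71 / 12 = 1.48).

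**Reading B: both arms timed from the concurrent workshop, as F2 says**

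A TAU Veteran takes the date of the workshop for which the ACT Veterans enrolled at the same time are waiting. If that date is scheduled ahead, randomisation gives both arms the same expected wait. Both 12-week visits fall at 12 weeks plus that wait, and the expected gap is 0.

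One refinement applies if the workshop is instead held the moment the ACT places fill. A TAU Veteran is then never the arrival that triggers it. With random arrivals, the mean wait is (g + 1) / (2 × 0.613) in TAU against (g − 1) / (2 × 0.613) in ACT. TAU waits 1 / 0.613 = 1.6 weeks longer, the opposite direction to reading A. That comes from a fill-to-start rule the document does not contain.

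**Reading C: both arms timed from randomisation**

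The gap is again 0. But with mean waits of 3.3 to 5.7 weeks, many ACT 2-week visits would come before the workshop.

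**Which reading the text supports**

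Reading B uses the anchor that F2 states for both arms. Readings A and C each replace it with one that no section names. For an ACT Veteran who does not attend, the workshop still has a date, and follow-up can run from it.

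**The case for a change.** The strongest case for a change is that no single workshop exists. With 80 enrolled and 10 in Pilot 1, 70 are randomised and about 47 go to ACT (70 × 2/3). At 5 to 8 per group that means roughly 6 to 9 workshops (47 / 8 = 5.9; 47 / 5 = 9.4), so someone must decide which date a TAU Veteran takes. Fixing this would cost one sentence and one logged date per Veteran. Pilot status is no excuse, because retention at 12 weeks also needs a defined week 12.

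The omission stands as a matter of wording: no section links a TAU Veteran to a particular workshop, covers non-attenders, or defines week. The follow-up forms that F2 calls attached are not in the file reviewed, so they cannot settle it either way.

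The inference to bias does not stand. It requires staff to leave the one stated anchor for another that appears nowhere. Even then, G2 treats week as continuous. If analysts entered actual time since baseline, the group-by-week term would compare rates of change and allow for unequal intervals, provided change is linear.

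The larger remedy is a trade-off, not a clear gain. Randomising in batches of nine would leave the first Veteran of a batch consented but unallocated for about (9 − 1) / 4 = 2 months, or 8.7 weeks (mean 4.3), with older baselines and a chance of dropout before allocation.

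G2 describes 2- and 6-week data for the four hypothesised outcomes, whereas the F2 lists place them only at baseline and 12 weeks. That is a separate inconsistency. The single-interval argument takes the F2 side of it, and nothing here resolves it.

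**Conclusion.** The concern does not call for a change. The document gives one anchor for both arms and omits only the sentence saying which workshop date a TAU Veteran or a non-attender takes. The natural choice is the concurrent scheduled workshop, which gives an expected difference of 0 weeks between arms when dates are set ahead. A definition of day 0 as that date would restate what F2 already implies, and a refit with actual assessment times would be a check, not a different analysis.

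The contrast of 15.3 to 17.7 weeks against 12 is correct arithmetic for a hypothetical. It depends on all four assumptions listed under reading A, and the decisive one, timing TAU from randomisation, departs from the text. The document gives no rate of background change, so neither the size nor the direction of any bias in the outcomes can be derived from it. The conclusion assumes that staff follow the stated anchor. It would change if conduct records showed TAU visits being counted from randomisation while ACT visits were counted from the workshop.

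### G2 analyses WHO-QOL, WHODAS-II, DASS-21 and BPI at four visits, but F2 collects them only at baseline and week 12

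*Combined protocol and SAP*

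**What the plan says.** The hypothesis in G2 is set at week 12: "We hypothesize that at 3-month follow-up, Veterans randomized to ACT on Life will experience greater improvements in Quality of life (WHO-QOL", and it goes on to name functioning (WHODAS-II), distress (DASS-21) and pain interference (BPI). The analysis sentence that follows reads "Data collected at baseline, 2-, 6- and 12-weeks follow-up for each of the aforementioned outcomes of interest will be compared between the groups". The method named there is a GLMM. The terms are then given: "The GLMM model for each outcome will include group, week (continuous outcome) and group by week interaction as the predictors". No other efficacy analysis is described.

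F2 lists the instruments visit by visit. The baseline self-report list holds the DASS-21 and the BPI, and also "The World Health Organization Disability Assessment Schedule II (WHODAS-II) - The World Health Organization-Quality of Life (WHO-QOL". The next two lists open with "At the 2-week follow-up, the following self-report measures will be completed: Chronic Pain Acceptance Questionnaire (CPAQ" and "At the 6-week follow-up, the following self-report measures will be completed: Chronic Pain Acceptance Questionnaire (CPAQ". They continue with process, coping, social and trauma measures, a Pain Intensity Scale, and therapy and medication usage. The week-12 list returns to the full battery: "Self-Report Measures. The Depression Anxiety and Stress Scale (DASS-21) -The PTSD CheckList", and further on "The Brief Pain Inventory (BPI) - The World Health Organization Disability Assessment Schedule II (WHODAS-II) - The World Health Organization-Quality of Life (WHO-QOL".

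**The concern.** The analysis relies on two visits at which the outcomes are not scheduled. This is not missing data in the sense G2 has in mind, which is loss to follow-up and missed interviews. Values that were never scheduled for anyone cannot be recovered by a mixed model.

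Aim 3 in Section D is preliminary efficacy, and this is the only model offered for it. If G2 stays as it is, whoever analyses the trial must choose a replacement for four outcomes after the data are in, with nothing in the plan to hold that choice to. G2's case for handling dropout is also weaker than it appears, because these outcomes have no interim values to draw on.

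**Working it through.** **Schedule against analysis.** Entries counted from the F2 lists:

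| Visit | Self-report entries | WHO-QOL | WHODAS-II | DASS-21 | BPI |
|---|---|---|---|---|---|
| Baseline | 22 | yes | yes | yes | yes |
| Week 2 | 16 | no | no | no | no |
| Week 6 | 13 | no | no | no | no |
| Week 12 | 20 | yes | yes | yes | yes |

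Each outcome has 2 scheduled measurements, where G2 assumes 4. The Pain Intensity Scale at weeks 2 and 6 is a separate entry and does not replace the BPI, which G2 names for pain interference.

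**What the model becomes.** With two visits, group, week and group by week fit the four group-by-visit means exactly. The interaction times 12 is the between-group difference in change from baseline to week 12.

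**Inputs for size.** Allocation is 2:1 (F1). Planned loss at week 12 is 10% (G2). The number randomised is 80 − 10 = 70 (G1) or 30 (Section D). Completers are 0.9 × 70 = 63, split 42:21, or 0.9 × 30 = 27, split 18:9. The documents give no correlations, so those below are assumed. The plan states no figure that depends on the number of visits. Standard errors are in SD units for week-12 completers.

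**Step 1: two visits against four, model as stated.**
- The mean of weeks {0, 2, 6, 12} is 5, and the centred sum of squares is 25 + 9 + 1 + 49 = 84.
- For {0, 12} it is 36 + 36 = 72.
- With a random intercept (compound symmetry), the SE ratio is √(84/72) = 1.08 at any correlation.
- If correlation decays exponentially with time, generalised least squares gives 1.00.

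**Step 2: change contrast against baseline-adjusted week 12.** With ρ the baseline-to-week-12 correlation, the variance per person is 2(1 − ρ) for change and 1 − ρ² after adjustment. The SE ratio is √((1 + ρ)/2), which is 0.866 at ρ = 0.5 and 0.922 at ρ = 0.7. At ρ = 0.5:
- 42:21: √(1/42 + 1/21) = 0.267, so the SE falls from 0.267 to 0.267 × 0.866 = 0.231.
- 18:9: √(1/18 + 1/9) = 0.408, so the SE falls from 0.408 to 0.354.

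**Step 3: would interim visits still help a common-baseline model?** Generalised least squares, two visits against four:
- Compound symmetry, ρ = 0.5: 0.231 against 0.222 (42:21) and 0.354 against 0.340 (18:9).
- Compound symmetry, ρ = 0.7: 0.191 against 0.181 (42:21).
- Exponential decay, ρ of 0.5 or more: equal to within 0.1%.

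Interim visits would therefore lower the SE by 0% to 5% at correlations of 0.5 to 0.7.

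**Step 4: linearity in week.** Suppose an effect of 0.50 is present by week 2 and sustained (assumed shape). Under compound symmetry, the four-visit linear-week model estimates 12 × 0.5 × (−3 + 1 + 7)/84 = 0.36. Under exponential decay at ρ = 0.5 it estimates 0.49. The two-visit contrast gives 0.50.

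**Step 5: dropouts.** At 10% loss, 0.1 × 70 = 7 (or 0.1 × 30 = 3) randomised Veterans would have a baseline value only.

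**The case against.** The stated terms can be fitted to baseline and week-12 data without alteration, and the hypothesis is about week 12, where all four instruments are collected. G1 already calls the trial underpowered for efficacy and gives feasibility as its purpose. No stated sample size, power or significance level depends on the interim visits. On that view the slip is a wrong visit list, and a minor one. This stands as a limit on the consequences, but the four-visit comparison still cannot be done and nothing else is specified.

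The gain from baseline adjustment would exist even if F2 and G2 agreed, so it does not measure the harm of the mismatch. That is correct. It is a reason to choose one rewrite over another once a rewrite is needed.

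The 0% to 8% range covers completers only. If the 7 of 70 lost at week 12 had supplied weeks 0, 2 and 6, the ratio in Step 1 would be about 1.08 to 1.09 under compound symmetry and 1.01 to 1.02 under exponential decay, at correlations of 0.5 to 0.7. In Step 3, compound symmetry at 0.8 gives a ratio of 1.06. Neither changes the conclusion.

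Finally, F2 says the follow-up forms are attached, and they are not among the documents. If they contain the four instruments, F2 is the section in error. F2 and G2 would still need to be reconciled.

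**Conclusion.** The concern holds. On the explicit lists in F2, the efficacy analysis in G2 cannot be carried out as described for any of its four outcomes. It should be corrected, but it does not threaten the trial: the 3-month comparison survives, and the precision lost against the model as stated is 0% to 8% among completers. The two-visit contrast also avoids the linear-in-week assumption. A Veteran without a week-12 assessment contributes only a baseline value, so inference rests on data being missing at random given baseline and group, which the plan should say. The contradiction itself depends on no assumption beyond the F2 lists being complete. The sizes depend on the assumed correlations and, for the linearity example, on the assumed shape of effect.

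**What to change.** Rewrite G2 to match F2:
- Analyse WHO-QOL, WHODAS-II, DASS-21 and BPI each as a baseline-adjusted between-group comparison at week 12, or by an equivalent two-visit mixed model with a common baseline mean.
- For these outcomes, remove the week-2 and week-6 data and the continuous week term. In the mixed-model form, a two-level visit term takes its place.
- State that week-12 values are assumed missing at random given baseline and group. A sensitivity analysis using the interim measures already collected is optional.

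The cost is a few sentences, using data already planned.

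If the sponsor does want repeated measures on these outcomes, the week-2 and week-6 batteries must be reconciled with G2 instead. That needs a schedule amendment and adds four questionnaires to visits already holding 16 and 13 entries, in follow-up assessments expected to last 1 hour. For the week-12 comparison, the return in precision would be small (Step 3). In either case, check the attached forms against F2 first.
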